- 1) Assess the frequency, quantity, and duration of viremia after a single dose of rZIKV/D4Δ30-713 given at either 10^3 PFU or 10^4 PFU.
- 2) Evaluate the number of vaccine recipients infected with either 10^3 PFU or 10^4 PFU rZIKV/D4Δ30-713. Infection is defined as recovery of infectious vaccine virus from the blood, serum, or urine of a subject and/or by seroconversion to ZIKV (plaque-reduction neutralization titer [PRNT₅₀] $\geq 1:10$) within the 90-day period following vaccination.
- 3) Determine the durability of antibody response 26 weeks after vaccination.
- 4) Determine the quantity and duration of ZIKV presence as determined by:
 - The peak virus titer in the blood and the duration of viremia induced by the LA Zika vaccine as determined by RT-PCR and virus culture
 - The quantity and duration of possible Zika vaccine shedding in urine determined by RT-PCR and virus culture
 - The quantity and duration of possible Zika vaccine shedding in vaginal secretions determined by RT-PCR and virus culture
 - The quantity and duration of possible Zika vaccine shedding in semen determined by RT-PCR and virus culture

Exploratory objectives:

- 1) To evaluate the phenotype of peripheral blood mononuclear cells (PBMCs) at primary infection with the rZIKV/D4Δ30-713 vaccine.
- 2) To evaluate the cellular immune response to primary infection with the rZIKV/D4Δ30-713 vaccine.
- 3) To evaluate the innate immune response to primary infection with the rZIKV/D4Δ30-713 vaccine.
- 4) To evaluate B and T cell memory responses following primary infection with the rZIKV/D4Δ30-713 vaccine.
- 5) To evaluate the antibody response in saliva to infection with rZIKV/D4Δ30-713 as a possible diagnostic tool. This will be done in a subset of subjects (those enrolled at the Center for Immunization Research [CIR]).

Primary Endpoints

Safety

Occurrence, intensity and relationship to vaccination of solicited local and general adverse events (AEs) within the 28-day follow-up period after vaccination.

Occurrence, intensity and relationship to vaccination of unsolicited AEs within the 28-day (Days 0-28) follow-up period after vaccination.

Occurrence of medically-attended adverse events and serious adverse events (SAEs) throughout the entire study period.

Immunogenicity

Determination of the peak neutralizing antibody titer to ZIKV through 90 days following vaccination with either 10^3 PFU or 10^4 PFU of rZIKV/D4 Δ 30.

Secondary Endpoint

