4.1.3 Duration of Subject Participation

Subjects will be followed for approximately 26 weeks (approximately 180 days) from the time of the initial inoculation. Subjects will be screened for eligibility up to 60 days prior to inoculation on Study Day 0.

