8. Obtain vaginal secretion sample (women) for virus isolation and culture. Vaginal cup may be inserted at home by the volunteer prior to presentation to the clinic.*
9. Obtain semen sample (men) for virus isolation and culture, which may be collected at home by the volunteer prior to presentation to the clinic.*
10. Obtain oral fluid for serology (CIR site only).

*Virology will be done on Study Day 90 only if virus was recovered from the sample collected at the previous time-point (Day 56).

Study Day 150 (+ 14 days)

1. Screening questions for COVID-19.
2. Perform interim history for interim complaints (physical exam is optional- will be done should subject have any medically-attended AEs since last visit or at the discretion of the investigator).
3. Record vital signs.
4. Obtain approximately 50 mL of blood for virology* and immunology (PBMCs, serum, and plasma).
5. For females, perform β -HCG testing.
6. Review pregnancy prevention with the subject.
7. Obtain urine sample for virus isolation and culture.*
8. Obtain vaginal secretion sample (women) for virus isolation and culture. Vaginal cup may be inserted at home by the volunteer prior to presentation to the clinic.*
9. Obtain semen sample (men) for virus isolation and culture, may be collected at home by the volunteer prior to presentation to the clinic.*
10. Obtain oral fluid for serology (CIR site only).

*Collection of urine, vaginal secretion, and semen samples and virology (urine, vaginal secretion, semen, blood) will be done on Study Day 150 only if virus was recovered from the sample collected at the previous time-point (Day 90) or if virology results are not available.

Study Day 180 (+ 28 / - 14 days)

1. Screening questions for COVID-19.
2. Perform interim history for interim complaints and focused physical exam, concentrating on any acute complaints.
3. Record vital signs.
4. Obtain approximately 50 mL of blood for immunology (PBMCs, serum, and plasma).
5. For females, perform β -HCG testing.
6. Obtain urine sample for virus isolation and culture.*
7. Obtain vaginal secretion sample (women) for virus isolation and culture. Vaginal cup may be inserted at home by the volunteer prior to presentation to the clinic.*
8. Obtain semen sample (men) for virus isolation and culture, may be collected at home by the volunteer prior to presentation to the clinic. *
9. Obtain oral fluid for serology (CIR site only).

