8.1.2 Medically-attended Adverse Event

A medically attended AE is defined as any visit (other than hospitalization, visit for routine health maintenance, or visit for a pre-existing condition that has not worsened) to an emergency room (ER), urgent care facility, doctor, nurse, or any other health care provider. Medically attended AEs from days 29 through 180 will be collected. Medically attended AEs that are found to be unrelated to the study product will be followed until resolution or the end of the study, whichever occurs first.

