8.1.6 Serious Adverse Event

A serious adverse event (SAE) is an AE that is determined to be “serious,” whether considered related to the investigational vaccine or not. SAEs will be collected for the duration of the trial. An SAE results in one or more of the following outcomes:

- Death during the period of protocol-defined surveillance
- A life-threatening event, defined as an event that places a subject at immediate risk of death at the time of the event and does not refer to an event that hypothetically might have caused death were it more severe
- Inpatient hospitalization or prolongation of existing hospitalization, defined as at least an overnight stay in the hospital or emergency room for treatment that would have been inappropriate if administered in the outpatient setting
- Congenital anomaly or birth defect
- Persistent or significant incapacity or substantial disruption of the ability to conduct normal life functions
- Other medically important events*

*Medical and scientific judgment should be exercised in deciding whether expedited reporting is appropriate in other situations, such as important medical events that may not be immediately

life-threatening or result in death or hospitalization but may jeopardize the subject or may require intervention to prevent one of the outcomes listed above. These will also usually be considered serious.

Each AE will be classified by the investigator/designee as serious or non-serious. An SAE needs to meet only one or more of the above criteria to be considered serious.

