8.3.2 Serious Adverse Events

Office of Clinical Research Policy and Regulatory Operations Clinical Safety Office

All SAEs (regardless of relationship and whether or not they are also unanticipated problems) must be reported according to the sponsor's reporting plan by using the REDCap system. Deaths and immediately life-threatening SAEs must be reported to the CSO within 1 business day after the site becomes aware of the event. All other SAEs must be reported within 3 working days of notification of the SAE occurrence to:

- REDCap website: <https://crimsonredcap.cc.nih.gov/redcap/index.php>
- OCRPRO CSO [contact], [contact], E-mail: [contact]

SAEs that have not resolved by the end of the follow-up period are followed until final outcome is known. If it is not possible to obtain a final outcome for an SAE (e.g., the subject is lost to follow-up), the reason a final outcome could not be obtained will be recorded by the investigator on the AE case report form and according to the sponsor's reporting guidelines.

SAEs that occur after the study follow-up period (study day 180) that are reported to and are assessed by the investigator to be possibly, probably, or definitely related to study drug must be reported to the CSO.

Data and Safety Monitoring Board

All SAEs must be reported by telephone (followed by written report), email, or fax within 1 working day of notification of the SAE occurrence to:

- The DSMB executive secretary – [contact], [contact], Email: [contact]

Johns Hopkins University Biosafety Committee

All SAEs must be reported by telephone (followed by written report), email, or fax within 1 working day of notification of the SAE occurrence to:

- The JHU Institutional Biosafety Committee: [contact], [contact]

Institutional Review Board Reporting

All SAEs will be reported to WIRB-Copernicus Group, Inc (WCG IRB) and UVM IRB as per guidelines, respectively, for JHU and UVM as below:

- **WCG IRB Guidelines:**

WCG IRB [contact], [contact]
www.wcgirb.com for updated reporting guidelines

- **UVM IRB Guidelines:**

- Investigators are required to report AEs that fit the following criteria:
 - Report timelines are based on the time the investigator or site personnel becomes aware of them:
 - A local death report within 48 hours
 - All other local AEs should be reported promptly, not to exceed 7 days
- Local AEs (whether or not they are serious) that are unexpected, and possibly, probably, or definitely related to study participation:

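### The final-visit window allows the last routine contact on Day 166, although medically attended AEs, part of the primary safety endpoint, are to be collected through Day 180

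*Combined protocol and SAP*

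**What the plan says.** The schedule in Section 7.4.1 gives the closing visit as "Study Day 180 (+ 28 / - 14 days". The visit before it is "Study Day 150 (+ 14 days". The Day 56 and Day 90 visits likewise have only a plus side (+14 and +10 days).

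The collection period for MAAEs is given in days, in Section 8.1.2: "Medically attended AEs from days 29 through 180 will be collected". The Precis lists, among the primary safety endpoints, "Occurrence of medically-attended adverse events and serious adverse events (SAEs) throughout the entire study period".

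For SAEs the text is looser. Section 8.1.6 says "SAEs will be collected for the duration of the trial". A day number appears only in a parenthesis in the reporting rules of Section 8.3.2: "SAEs that occur after the study follow-up period (study day 180) that are reported to". Section 4.1.3 describes overall follow-up as approximate: "Subjects will be followed for approximately 26 weeks (approximately 180 days) from the time of the initial inoculation".

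After Day 28, Section 7.7 relies on updates of the medical history to find MAAEs, and Section 7.4.1 obtains these through the interim history taken at each visit. Section 10.6.1 puts every subject into the safety analysis however many visits were missed. Section 10 has no rule for a final visit that falls before or after Day 180.

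**The concern.** Two stated rules do not fit together. One says that MAAEs are collected through Day 180. The other lets the visit that closes this collection take place two weeks before Day 180.

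A minus side on an earlier visit does no harm, because the next visit covers the days that were skipped. The Day 180 visit is different: nothing routine follows it. The plan is careful to allow only late attendance at Days 56, 90 and 150, then allows early attendance at the one visit where it leaves a gap.

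The study is descriptive, and its output is event frequencies. A frequency needs a defined period of observation, and here that period can be shorter for some subjects than the plan states.

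**Working it through.** **Inputs**
- Final visit: nominal Day 180, minus 14, plus 28 (Section 7.4.1).
- MAAE collection: Days 29 to 180 (Section 8.1.2).
- Follow-up: about 26 weeks, about 180 days (Section 4.1.3).
- Subjects: up to 56, of whom 40 receive vaccine and 16 placebo (Section 4.1.2).
- MAAE risk over Days 29 to 180: not in the documents. Assumed 5 to 40%, with a constant hazard.

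**The plan's own figure.** 26 × 7 = 182 days, which agrees with the stated approximate 180.

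**Window.** Earliest visit: 180 − 14 = Day 166. Latest: 180 + 28 = Day 208. The Day 150 visit can be as late as 150 + 14 = Day 164, so the last two visits, nominally 30 days apart, can be 2 days apart.

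**Days not queried after a Day 166 visit**
- MAAE period: 180 − 29 + 1 = 152 days.
- Covered: 166 − 29 + 1 = 138 days.
- Not covered: 152 − 138 = 14 days, and 14/152 = 9.2%.
- For SAEs, if Day 180 is taken as the end: 14/180 = 7.8%.

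**Effect on the measured risk.** With true risk p over 152 days and a constant hazard, the risk observed over 138 days is 1 − (1 − p)^(138/152). This supposes that no event in the last 14 days reaches the site by another route. The last column multiplies the shortfall by 40, as if every vaccinee attended on Day 166.

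| True risk p | Observed risk | Shortfall (points) | Vaccinees with a missed first event, of 40 |
|---|---|---|---|
| 5% | 4.55% | 0.45 | 0.18 |
| 10% | 9.12% | 0.88 | 0.35 |
| 20% | 18.34% | 1.66 | 0.66 |
| 40% | 37.11% | 2.89 | 1.16 |

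Over all 56 subjects the same extreme gives 0.25 to 1.62.

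**After the change.** With no minus side the earliest visit is Day 180, and all 152 days are covered. A contact on or after Day 180 for anyone seen earlier gives the same result.

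**The case against.** The best defence is that Day 180 is a nominal label. Follow-up is described as approximate, the Precis speaks of the whole study period, and SAEs are tied to the duration of the trial. On that reading, a visit inside its window completes the period. This carries real weight for SAEs. It does not settle the matter for MAAEs, because Section 8.1.2 names the days.

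A second defence is that scheduled visits are not the only source of information. Section 8.2.1 gives subjects 24-hour access to a clinician during the evaluation period. Section 10.3 counts passive as well as active surveillance. Section 7.4.1.1 brings back subjects who still shed vaccine virus, and Section 8.3.2 still requires related SAEs reported after follow-up to go to the sponsor's safety office. It would therefore be wrong to infer that a Day 166 attender has no possible later contact. What stands is that none of these routes routinely asks such a subject about Days 167 to 180.

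Third, the effect is small and the assumed risks have no support in the documents. Section 10.3 also centres the primary safety endpoint on vaccine-related AEs, which Section 8.2.1 expects by Day 28. This is correct, and it limits the point to a minor one.

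Finally, a plus-only window would put early attenders out of window. That is a fair practical cost, and the telephone option avoids it.

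**Conclusion.** The mismatch is real for MAAEs and weaker for SAEs. A subject who follows the protocol can leave up to 14 of 152 days (9.2%) of a stated primary collection period without active questioning. On the assumed 5 to 40% risk and constant hazard, the measured risk for that subject is about 0.45 to 2.9 points low. The worst case is about 0.2 to 1.2 of 40 vaccinees, and less in practice, since not everyone will attend on the earliest day. The same window applies to both arms, so the rule itself gives no reason to expect a distorted comparison. This is a cheap improvement and no threat to the trial's conclusions.

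Three stronger readings are tempting, and the documents do not support them:
- A reader might infer that early attenders are tabulated as free of events through Day 180. Section 10.6.1 says only that they are included; no passage says how a shortened follow-up is shown.
- A reader might take the full spread from Day 166 to Day 208 as a 42-day imbalance that biases the proportion in both directions. That combines two incompatible readings. If collection ends at Day 180, MAAEs on Days 181 to 208 fall outside it and the largest difference is 14 days. If the whole study period governs, Day 180 is not a fixed end. The plan does need to say which applies.
- A reader might extend the point to the 26-week antibody titer. The window does span weeks 23.7 to 29.7 (166/7 to 208/7), but the documents give no rate of antibody decline from which to size an effect. A plus-only window would still leave a 28-day spread.

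**What to change.** Reconcile Section 7.4.1 with Section 8.1.2 in one of two ways:
- make the Day 180 window plus-only (0/+28 days), in line with Days 56, 90 and 150; or
- keep the −14 side and add a telephone check for MAAEs and SAEs on or after Day 180 for anyone seen earlier.

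With either choice, add to Section 10 that MAAEs and SAEs with onset through Day 180 are tabulated for all subjects, that later events are listed separately, and that the number of subjects whose last contact came before Day 180 is reported. State the same end day for SAEs in Sections 8.1.6 and 8.3.2.

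The cost is slightly less freedom in booking the last visit, or one brief call for each early attender.

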7.4.1.1 Persistence of Zika Vaccine in Bodily Fluids

If Zika vaccine is detected in any bodily fluid at Study Day 180, the subject will continue to be followed until Zika vaccine is no longer detected in the bodily fluid. To achieve this, the subject

will be brought back for unscheduled visits for collection of the specimen of interest (the bodily fluid that was positive for Zika vaccine at Study Day 180) and for review of clinical symptoms. If clinical symptoms are reported, the subject will undergo clinical evaluation. Persistent shedding of Zika vaccine in bodily fluids at Study Day 180 will be reported to the DSMB and the FDA as soon as it is detected. The DSMB and the FDA will be asked to provide additional guidance as to follow-up procedures, the interval of specimen collection, and the duration of specimen collection.

7.5 Subject Temperature Memory Card

Subjects will be provided with a thermometer and a Temperature Memory Card to use as a memory aid and will be asked to record temperatures 2 times a day from study day 0 through study day 16 post-inoculation. Study staff will review the subjects' temperature cards on study day visits 4 through 21 to assess for any fevers and compare subject recordings to the study visit temperatures. Staff will record all temperatures recorded by the subject and will also separately record the maximum temperature for each date (T_{max}) on the source document. Subject memory cards will not be collected by the study staff as subject's recordings will not be considered required data.

Staff will instruct subjects on how to use the thermometers, to take their temperatures at approximately the same time each day, and to take additional temperatures if they feel they have elevated temperatures. Subjects will be asked to wait at least 15 minutes after eating, drinking, and smoking before taking their temperatures. They will be asked to confirm an elevated temperature ($\geq 100.4^{\circ}\text{F}$) by retaking the temperature after a 20-minute interval and at 1 hour. Temperatures not documented to last at least 1 hour will not be considered an AE or included in the analysis.

7.5.1 Notification of Staff of Zika-like Symptoms

Subjects will be asked to call or otherwise contact the study staff should they experience any symptoms of Zika illness. The Zika-like illness symptoms that study staff will review with the subjects are the systemic reactogenicity signs included in [Table 9](#). Once notified, study staff will arrange to evaluate the subject at the earliest convenience; this may result in an unscheduled visit for the subject.

7.5.2 Notification of Staff of COVID-19-like symptoms

Subjects will be asked to call or otherwise contact study staff should they experience any COVID-19 symptoms. In addition, at each visit, volunteers will be asked whether or not they have experienced any COVID-19 symptoms (per facility guidelines) or if they have had an exposure to someone with COVID-19 prior to coming into the clinic. If the volunteer reports symptoms consistent with COVID-19 and they are already enrolled in the study, an NP or mid-turbinate swab will be collected and tested for COVID-19 on site or at a local laboratory at any time. The volunteer will not come into the clinic until the result is confirmed to be negative. Should a volunteer test positive for SARS-CoV-2 at any point during the study, the volunteer will be asked to quarantine according to current CDC guidelines. We will review current CDC guidelines with the volunteer. We will defer all in-person visits until after the volunteer has completed their quarantine or see them in a COVID-19 positive research space if it is available. If they test positive for SARS-CoV-2 during the first 21-days post-vaccination, scheduled follow-up visits will be done as telehealth visits or in a COVID-19 positive research space.

7.6 Clinical Laboratory Testing

Using standard techniques, Quest Diagnostics or other CLIA-certified laboratories will perform the following tests:

1. CBC plus WBC differential
2. PT/PTT
3. ALT, AST, alkaline phosphatase, total bilirubin, creatinine
4. HIV assay (screening antibody assay with confirmation for positive antibody assays).
5. Hepatitis B screening by testing for HBsAg
6. Hepatitis C screening by testing for hepatitis C antibody. If positive, the test is confirmed by testing for hepatitis C RNA. If hepatitis C antibody is positive but RNA is negative, the subject is assessed as having a past infection that has cleared. In this case, the subject is eligible for the study.
7. Urinalysis (in the event of an abnormal urine dipstick test)
8. SARS-CoV-2 PCR testing
9. Serum β -HCG, if required

Urine and serum β -HCG testing will be performed at the clinical trial site using an FDA-approved pregnancy test kit. Urine dipstick testing will be performed at the clinical trial site using an FDA-approved product. Rapid HIV testing may be performed at the clinical trial site using an FDA-approved test kit. Determination of vaccine virus titer, plaque reduction neutralization antibody assays, and cellular immune studies will be done at the clinical trial site laboratory.

7.7 Medical History and Concomitant Medications

A complete medical history will be collected during screening. Any changes reported in medical history during the 28-day post-inoculation period will be assessed as possible AEs. After study day 28, the medical history will be updated for any new or changed significant or chronic conditions, and to identify if any medically attended AEs have occurred.

Study staff will collect current medications as part of the medical history, including over-the-counter medications and herbal supplements, at the time of enrollment. All changes or updates to medications will be collected through study day 28 following inoculation. After study day 28, concomitant medications will be collected to identify new or changed significant or chronic conditions. Medications taken for AEs continuing after study day 28 will be recorded throughout the trial.

7.8 Immunology Testing

7.8.1 Antibody Testing

Serum antibody levels to ZIKV will be measured by plaque reduction neutralizing antibody assay using standard laboratory protocols. The PRNT₅₀ is defined as the highest dilution of antibody that reduces the number of foci or plaques by 50%, compared to the plaque titer of the virus alone.

